## 12. ADVERSE EVENTS

### 12.1. Definition of Adverse Events

#### 12.1.1. Adverse Event

An AE is any untoward medical occurrence in a clinical study subject. No causal relationship with the study drug/IMP or with the clinical study itself is implied. An AE may be an unfavorable and unintended sign, symptom, syndrome, or illness that develops or worsens during the clinical study. Clinically relevant abnormal results of diagnostic procedures including abnormal laboratory findings (eg, requiring unscheduled diagnostic procedures or treatment measures, or resulting in withdrawal from the study) are considered to be AEs. Abnormal results of diagnostic procedures that are incidental or not clinically relevant are not reportable as AEs. If the diagnostic procedure prompts no additional treatment, visits, or monitoring, it will not meet the definition of an AE.

This includes the following:

- AEs not previously observed in the subject that emerge during the protocol-specified AE reporting period (see Section 12.4.1).
- Findings from protocol-mandated interventions. This can include laboratory assessments performed in the course of the clinical study. AEs should be reported only if the abnormalities are changes from baseline and are clinically significant as described above.
- Pre-existing medical conditions (other than the condition being studied) judged by the investigator to have worsened in severity or frequency or changed in character during

the protocol-specified AE reporting period. When recording such events on an AE/SAE eCRF page, it is important to convey the concept that the pre-existing condition has changed by including applicable descriptors (eg, “more frequent headaches”).

An adverse reaction is defined in International Council for Harmonisation (ICH) E6 guideline as follows: all untoward and unintended responses to a study drug/IMP related to any dose administered. The definition covers also medication errors and uses outside what is foreseen in the protocol, including misuse and abuse of the product. The definition implies a reasonable possibility of a causal relationship between the event and the study drug/IMP. This means that there are facts (evidence) or arguments to suggest a causal relationship.

Hospitalization scenarios do not require reporting as an SAE where there is no occurrence of an AE. These scenarios include a planned hospitalization or prolonged hospitalization to:

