- Perform a routine control screening for a pre-existing illness or to diagnose a suspected illness. In the case of the latter, the symptomatology should be reported as an AE and amended if a diagnosis is confirmed.
- Undergo a diagnostic or elective surgical procedure for a pre-existing medical condition that has not changed (eg, a joint replacement for which the subject was on a waiting list).
- Undergo medical observation without the occurrence of an AE due to standard of care in the region or hospital.

Surgical procedures should not be reported as AEs. The condition for which the surgery is required should be reported as the AE if it occurs or is detected during the study period. Planned surgical measures permitted by the clinical study protocol and the conditions(s) leading to these measures are not AEs if the condition(s) was (were) known before the start of study treatment. In the latter case, the condition should be reported as medical history.

AEs are designated as “nonserious” or “serious”.

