### **12.1.2. Serious Adverse Event**

A serious adverse event (SAE) is an AE/reaction that results in any of the following outcomes:

- Death
- Is life-threatening (subject is at immediate risk of death at the time of the event; it does not refer to an event that hypothetically might have caused death if it were more severe)
- Requires subject hospitalization (formal admission to a hospital for medical reasons) or prolongation of existing hospitalization
- Results in persistent or significant disability/incapacity (ie, there is a substantial disruption of a person’s ability to carry out normal life functions)
- Is a congenital anomaly/birth defect

Important medical events that may not result in death, are not life-threatening, or do not require hospitalization may be considered SAEs when, based upon appropriate medical judgment, they may jeopardize the subject’s health or may require medical or surgical intervention to prevent one of the outcomes listed in this definition. Examples of such events

may include allergic bronchospasm requiring intensive treatment in an emergency room or at home, blood dyscrasias, or convulsions that do not result in subject hospitalization.

In addition, the sponsor considers any abortions (elective or spontaneous), fetal demise, and still birth to be SAEs for reporting purposes (see Section 12.4.2).

Some hospitalization scenarios, as outlined in Section 12.1.1, do not require reporting as SAEs.

Overdose will be considered an SAE only if any of the seriousness criteria are met. Any clinical complication in association with the overdose should be reported as an AE or SAE (as applicable) along with the overdose (see Section 12.6). Details of signs or symptoms, clinical management, and outcome should be reported, if available. Overdose without associated signs or symptoms should not be recorded as AEs but should be recorded as protocol deviations.

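### Protocol 12.1.1 lists diagnostic hospital stays under an SAE exemption for cases without an AE, yet calls their symptoms an AE, so sites can record an AE that meets the 12.1.2 hospitalization criterion as non-serious

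*Protocol*

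**What the plan says.** Protocol Section 12.1.1 states the exemption with a condition attached: "Hospitalization scenarios do not require reporting as an SAE where there is no occurrence of an AE". It continues: "These scenarios include a planned hospitalization or prolonged hospitalization to", followed by three bullets. The first covers a routine check of a known illness and also a stay "to diagnose a suspected illness. In the case of the latter, the symptomatology should be reported as an AE", with the record to be amended once a diagnosis is confirmed. The second covers a diagnostic or elective surgical procedure for an unchanged pre-existing condition. The third is "Undergo medical observation without the occurrence of an AE due to standard of care in the region or hospital".

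Protocol Section 12.1.2 gives as one seriousness criterion: "Requires subject hospitalization (formal admission to a hospital for medical reasons) or prolongation of existing hospitalization". Later in the same section it says: "Some hospitalization scenarios, as outlined in Section 12.1.1, do not require reporting as SAEs".

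Protocol Sections 12.4 and 12.4.1 require SAEs to reach the sponsor within 24 hours. Section 13.3.4 names the proportion of subjects with a treatment-emergent SAE among five minimum safety results. The SAP tabulates serious and non-serious TEAEs separately (Sections 8.2.2.1 and 8.2.2.2; Tables 14.3.2.3.1 and 14.3.2.3.2) and lists SAEs in Listing 16.2.7.2.

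**The concern.** The diagnostic stay is placed under a condition that it fails by its own terms: the exemption needs the absence of an AE, and the bullet declares one. Because Section 12.1.2 refers back to that list, the conflict enters the SAE definition itself. Two careful sites could classify the same event differently, and each could point to the protocol in support.

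The seriousness label drives two things. The first is the 24-hour report; the sponsor's 7- and 15-day SUSAR timelines run from its own knowledge of the case, so a late report can also delay those. The second is the main output of the study. Safety is its only endpoint domain, there are at most 30 subjects, and the SAE proportion is a required result. SAP Section 5.7.2 has a default for missing severity and missing relationship, but the SAP has no rule or check on seriousness. The site's choice therefore goes straight into the tables.

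**Working it through.** The plan states no figure on this point, so the check is a comparison of texts followed by a statement of scale.

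**Step 1. Does each listed case satisfy the no-AE condition?**

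| Listed case (Protocol 12.1.1) | Its own limit | Satisfies the condition? |
|---|---|---|
| Routine control of a known illness | Pre-existing illness, routine check | Yes, unless something new is found |
| Work-up of a suspected illness | None; its symptoms are to be reported as an AE | No, by its own wording |
| Diagnostic or elective procedure | Pre-existing condition must be unchanged | Yes |
| Observation under local standard of care | No AE, stated again | Yes |

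Only the work-up case exempts a hospital stay while declaring an AE.

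**Step 2. Apply both rules to one event.** Take an AE of symptoms that leads to a formal admission, or to a longer stay, for diagnosis.

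- Reading A, the list governs: the stay is among the exempt scenarios, 12.1.2 defers to that list, and the AE is recorded as non-serious.
- Reading B, the opening condition governs: an AE has occurred, so the exemption falls away, and the AE is serious under 12.1.2 if it required or prolonged the hospitalization.

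No sentence in the protocol ranks one reading above the other. The bullet has the record amended once a diagnosis is confirmed, and Section 12.4 likewise has the diagnosis replace the symptoms. Neither asks for seriousness to be assessed again at that point.

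**Step 3. Scale.** Inputs: a planned maximum of 30 subjects (Protocol Sections 7.2 and 13.1), and the safety population as denominator (SAP Section 8.2.2.1). The serious-TEAE table counts subjects with at least one event, so the proportion falls by 1/N only when the affected subject has no other serious TEAE.

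- N = 30: 1/30 = 3.3 percentage points.
- N = 20 (assumed): 1/20 = 5.0 points.
- N = 15 (assumed): 1/15 = 6.7 points.

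The non-serious table need not rise by the same amount. A subject can appear in both tables, and its overall subject count grows only if the subject has no other non-serious TEAE. The documents give no number of diagnostic admissions, so the total undercount cannot be estimated.

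**The case against.** A coherent reading is available. On it, a diagnostic admission is not an SAE merely because it is an admission; its symptoms are recorded as an AE, and that AE is then classed as serious or non-serious under 12.1.2 like any other. Section 12.1.1 does close by saying that AEs receive one of those two labels, and nowhere does it state that the symptom AE is non-serious. This reading is possible, but nothing in the text makes it prevail, and the cross-reference in 12.1.2 invites the other one.

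A reader might go further and infer that acute admissions for invasive infection, hemolysis, or renal or hepatic injury escape 24-hour reporting. The documents do not support that:

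- An unplanned acute admission is not a planned one, so that limb of the exemption does not reach it. Prolongation of an existing stay remains exposed.
- Life-threatening events, and important medical events (with blood dyscrasias as an example), are SAEs under 12.1.2 on other grounds.
- The sponsor's medical monitor should be told of hemolysis symptoms and of permanent discontinuation (12.5.3). Invasive meningococcal or encapsulated bacterial infection leads to permanent discontinuation (7.4.1). The hepatic discontinuation criteria call for discussion with the monitor (12.5.1).
- The list of events of special monitoring (12.1.3) and the renal detail (12.5.2) are blacked out, so a further reporting route cannot be ruled out.
- Renal and hepatic TEAEs have their own SAP tables whatever their seriousness.

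It is also fair that an elective work-up admission does not always mean that the AE required hospitalization. All of this narrows the exposure. None of it settles which rule governs, and notifying the monitor is not the same as an SAE report.

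**Conclusion.** The two sections conflict and need to be reconciled. The conflict in wording is certain; the harm is conditional. Such AEs can be recorded as non-serious, and sites may differ. It would be too strong to say that they will be, because that is only one of two readings. The exposure lies mainly in prolonged stays and planned work-up admissions where no other seriousness criterion applies. The size is 3.3 percentage points of the serious-TEAE proportion per affected subject, assuming that all 30 planned subjects are dosed and that the subject has no other serious TEAE; with fewer subjects it is larger. The number of affected subjects is unknown. The point is worth correcting because the rule bears on a required safety result in a small study and the correction is short.

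**What to change.** In Protocol Section 12.1.1, remove the diagnosis of a suspected illness from the exempt purposes, but keep the instruction to report the symptoms as an AE and to amend the record on diagnosis. Add one sentence, for example: an AE that leads to or prolongs a hospital stay for diagnostic work-up is assessed for seriousness under Section 12.1.2, and assessed again when the diagnosis is confirmed. A site memo can carry the clarification until the protocol text is changed.

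Before database lock, review every AE marked non-serious where a hospital admission is known. The eCRF is not among the documents, and admission details may sit only on the SAE form. If the AE page does not capture admission, use the source data verification already planned in Protocol Section 14.1. This review corrects the tables and listing even if the clarification comes too late to affect reporting.

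The cost is one clarification, one data-review query, possibly a few more SAE forms, and a slightly higher SAE count.

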### **12.1.2. Serious Adverse Event**

A serious adverse event (SAE) is an AE/reaction that results in any of the following outcomes:

- Death
- Is life-threatening (subject is at immediate risk of death at the time of the event; it does not refer to an event that hypothetically might have caused death if it were more severe)
- Requires subject hospitalization (formal admission to a hospital for medical reasons) or prolongation of existing hospitalization
- Results in persistent or significant disability/incapacity (ie, there is a substantial disruption of a person’s ability to carry out normal life functions)
- Is a congenital anomaly/birth defect

Important medical events that may not result in death, are not life-threatening, or do not require hospitalization may be considered SAEs when, based upon appropriate medical judgment, they may jeopardize the subject’s health or may require medical or surgical intervention to prevent one of the outcomes listed in this definition. Examples of such events

may include allergic bronchospasm requiring intensive treatment in an emergency room or at home, blood dyscrasias, or convulsions that do not result in subject hospitalization.

In addition, the sponsor considers any abortions (elective or spontaneous), fetal demise, and still birth to be SAEs for reporting purposes (see Section 12.4.2).

Some hospitalization scenarios, as outlined in Section 12.1.1, do not require reporting as SAEs.

Overdose will be considered an SAE only if any of the seriousness criteria are met. Any clinical complication in association with the overdose should be reported as an AE or SAE (as applicable) along with the overdose (see Section 12.6). Details of signs or symptoms, clinical management, and outcome should be reported, if available. Overdose without associated signs or symptoms should not be recorded as AEs but should be recorded as protocol deviations.

### 12.1.3. Events of Special Monitoring

Events of special monitoring (EOSM) are AEs or safety topics for which special monitoring, additional data collection activities, and/or enhanced signal detection activities within BioCryst are considered appropriate for this population and study. Identified EOSMs can be of particular concern based on findings from the IMP clinical program to date, potential and/or known risks generally associated with the underlying disease, or comorbidities and risk factors prevalent in the study population.

EOSM for this study include CCI [REDACTED]

CCI [REDACTED]

CCI [REDACTED]

## 12.2. Definition of Severity

All AEs will be assessed (graded) for severity by the investigator and classified using the US National Cancer Institute (NCI) Common Terminology Criteria for Adverse Events (CTCAE) (Version 5.0, published 27 November 2017). The NCI CTCAE is a descriptive terminology that can be used for AE reporting. The CTCAE displays Grades 1 through 5 with unique clinical descriptions of severity for each AE based on the following general guideline:

**Mild:** (Grade 1): Mild; asymptomatic or mild symptoms; clinical or diagnostic observations only; intervention not indicated.

**Moderate:** (Grade 2): Moderate; minimal, local or noninvasive intervention indicated; limiting age-appropriate instrumental ADLa.

**Severe:** (Grade 3): Severe or medically significant but not immediately life-threatening; hospitalization or prolongation of hospitalization indicated; disabling; limiting self-care ADLb.

**Life-threatening:** (Grade 4): Life-threatening consequences; urgent intervention indicated.

**Death** (Grade 5): Death related to AEc.

Abbreviations: ADL = activities of daily living; AE = adverse event.

a Instrumental ADL refer to preparing meals, shopping for groceries or clothes, using the telephone, managing money, etc.

b Self-care ADL refer to bathing, dressing and undressing, feeding self, using the toilet, taking medications, and not bedridden.

c Grade 5 (Death) is not appropriate for some AEs and therefore is not an option.

It is important to distinguish between serious and severe AEs. Severity is a measure of intensity, as defined above, whereas seriousness is defined by the criteria under Section 12.1.2. An AE of severe intensity may or may not be considered serious.

### 12.3. Relationship to Study Drug

An investigator who is qualified in medicine must make the determination of relationship to the study drug/IMP for each AE (not related, unlikely related, possibly related, probably related, definitely related). The investigator should decide whether, in his or her medical judgment, there is a reasonable possibility that the event may have been caused by the investigational product. If no valid reason exists for suggesting a relationship, then the AE should be classified as “not related”. If there is any valid reason, even if undetermined, for suspecting a possible cause-and-effect relationship between the study drug/IMP and the occurrence of the AE, then the AE should be considered “related”.

Not Related:	The event can be readily explained by other factors such as the subject's underlying medical condition, concomitant therapy, or accident, and no temporal relationship exists between the study drug/IMP and the event.
Unlikely Related:	The event does not follow a reasonable temporal sequence from drug administration and is readily explained by the subject's clinical state or by other modes of therapy administered to the subject.
Possibly Related:	There is some temporal relationship between the event and the administration of the study drug/IMP and the event is unlikely to be explained by the subject's medical condition, other therapies, or accident.
Probably Related:	The event follows a reasonable temporal sequence from study drug/IMP administration, abates upon discontinuation of the study drug/IMP, and cannot be reasonably explained by the known characteristics of the subject's clinical state.
Definitely Related:	The event follows a reasonable temporal sequence from study drug/IMP administration, follows a known or suspected response pattern to the study drug/IMP, is confirmed by improvement upon stopping the study drug/IMP (dechallenge), and reappears upon repeated exposure (rechallenge, if rechallenge is medically appropriate).

If the relationship between the (S)AE and the investigational product is determined to be “possible”, “probable”, or “definite”, the event will be considered to be related to the study drug/IMP for the purposes of expedited regulatory reporting (as applicable per country-specific regulatory requirements).

The sponsor may upgrade causality if deemed appropriate.

### 12.4. Method, Frequency, and Time Period for Detecting Adverse Events and Reporting Serious Adverse Events

Reports of all AEs and SAEs, regardless of investigator attribution, are to be collected from the time of enrollment through to the last study visit (ie, through the post-treatment follow-up

visit). If AEs/SAEs occur after the subject has signed the informed consent form (ICF) for Study 205 but while the subject is still enrolled in the prior study, the AEs/SAEs will be collected according to the procedures specified in the prior study protocol. All AEs and SAEs are to be reported on the AE eCRF.

AEs should be documented on the eCRFs as investigators become aware of them. AEs are to be followed until the event resolves. If an event is ongoing at the last follow-up visit, Grade 1 and Grade 2 events do not need to be followed if the event is deemed unlikely to be related or not related to study drug/IMP (see Section 12.2 for AE grading). For all Grade 3 and Grade 4 events or events deemed possibly, probably, or definitely related to use of study drug/IMP, the event should be followed until the AE is resolved or the subject is in a clinically stable condition with regard to the AE.

The investigator shall report all SAEs immediately and no later than 24 hours of their knowledge of the event to the sponsor by communicating with the medical monitor (phone or email) and by entering the event into the AE eCRF and by completion of the SAE eCRF. The SAE eCRF is an additional form to the AE eCRF that provides important details on the SAE. The investigator should follow all unresolved SAEs observed during the study until they are resolved, or are judged medically stable, or are otherwise medically explained.

The investigator should attempt, if possible, to establish a diagnosis based on the presenting signs and symptoms. In such cases, the diagnosis should be documented as the AE and not the individual sign/symptom. If a clear diagnosis cannot be established, each sign and symptom must be recorded individually. Once a diagnosis is made during evaluation or treatment, the investigator will update the AE record with this diagnosis and delete the previously reported signs and symptoms. The rapid reporting of SAEs ensures that the sponsor shall have the necessary information to continuously assess the benefit-risk profile of the study drug in clinical studies.

#### **12.4.1. Serious Adverse Events and Suspected Unexpected Serious Adverse Reactions**

The investigator must report all SAEs immediately and in no case later than within 24 hours of their knowledge of the event. Investigators should adhere to their country or region requirements for the reporting timeframe, which may not allow any delay. SAEs should be reported to the sponsor medical monitor and via the AE and SAE eCRFs. The SAE eCRF is an additional form to the AE eCRF that provides important details on the SAE. All additional follow-up evaluations of the SAE must be reported to BioCryst or its designee as soon as they are available by amending these eCRFs.

In the event the eCRF system is not functioning, the reporting of an SAE must not be delayed. Sites will have SAE report forms (electronic Word document) that can be completed and emailed to the below recipient. As soon as the eCRF system is functioning, that particular SAE must be entered into the AE eCRF. The eCRF system automatically sends SAE notifications to the following email address: [[contact]](mailto:[contact]).

Immediate reporting should allow BioCryst to take the appropriate measures to address potential new risks in a clinical study. Therefore, the initial report should be submitted by the investigator within a very short period of time and under no circumstances should this period exceed 24 hours following awareness of the SAE.

The follow-up report should allow BioCryst to determine whether the SAE requires a reassessment of the benefit-risk profile of the study drug/IMP in clinical study, if the relevant information was not already available and provided in the initial report.

Country-specific rules and requirements for safety management will be described in the Safety Management Plan prepared for this study.

Investigators or designees at each site are responsible for retaining copies of all suspected unexpected serious adverse reaction (SUSAR) reports (initial and follow-up) and other safety information (eg, revised IB) in the investigator site files.

BioCryst shall ensure that all relevant information about SUSARs that are fatal or life-threatening is recorded and reported as soon as possible to all competent authorities, and to the applicable ethics committee in any case no later than 7 calendar days after knowledge by BioCryst of such a case, and that relevant follow-up information is subsequently communicated within an additional 8 days. All other SUSARs shall be reported to the competent authorities concerned and to the ethics committees, as applicable, according to local regulations, as soon as possible but in no case later than 15 calendar days of first knowledge by BioCryst. BioCryst or designee shall also inform the investigator. **CCI**

